8.8.3.2. Time to Progression (TTP)

Time to progression (TTP) is defined as the duration from start of treatment to PD (earliest occurrence), with deaths from causes other than progression not counted, but censored. The calculation for the time of PD and censoring rules are the same as those for DCB (see Table 4).

TTP Event (day) = Date of progression – Date of first study treatment

TTP Censor (day) = Date of censoring – Date of first study treatment + 1

The same analyses will be done for TTP as those for DCB described in Section 8.7.2.1.

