2.5	Death from causes other than progression	Date of death	Censored

For subjects who meet more than one censoring condition, DCB will be censored according to the earliest censoring condition. For subjects who meet none of the censoring conditions, DCB will be calculated using the earliest event date.

$$\text{DCB Event (day)} = \text{Date of event} - \text{Date of first overall response}$$

$$\text{DCB Censor (day)} = \text{Date of censoring} - \text{Date of first overall response} + 1$$

Kaplan-Meier curves will be used to estimate the distribution of DCB. The 50th percentile of Kaplan-Meier estimates will be used to estimate the median DCB. A 2-sided 95% CI will be provided for this estimate. For the cases in which the median is not reached as if the study closure, the 25th percentile and its 2-sided 95% CI will be provided.

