8.8.2.3. Duration of Response (DOR)

DOR will include only subjects with confirmed responses (PR or better). DOR will be calculated from the first observation of response (before confirmation) to the time of PD (earliest occurrence), with death from causes other than progression censored. The calculation for the time of PD and censoring rules are the same as those for DCB (see Table 3).

DOR Event (day) = Date of event – Date of first overall response

DOR Censor (day) = Date of censoring – Date of first overall response + 1

The same analyses will be done for DOR as those for DCB described in Section 8.7.2.1.

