8.8.3. Exploratory Efficacy Endpoints

8.8.3.1. Progression-free Survival (PFS)

PFS is defined as the duration from the start of study treatment to PD (earliest occurrence) or death (regardless of cause of death), whichever comes first. The calculation for the time of PD will be the same as that for DCB (Section 8.7.2.1).

PFS will be right-censored for subjects who meet one or more of the censoring conditions listed in Table 5 below.

Table 5: Date of Event and Censoring Rules for PFS Analysis

Row	Situation	Date of Event or Censoring	Outcome
Events include death or first documentation of confirmed PD that occurred on or prior to the data analysis cutoff date. For Cohorts 1 and 3 ibrutinib monotherapy, events need to meet one additional criterion: occurred at or prior to initiation of dexamethasone.			
1.1	Death or confirmed PD documented at scheduled disease assessments or between two scheduled disease assessments.	Earliest date of adequate disease assessment documenting confirmed PD or date of death due to progression, whichever occurs first.	Progressed
1.2	Death before first disease assessment	Date of death	Progressed
All other cases will be censored as follows:			
2.1	No baseline assessment	Date of first study treatment	Censored
2.2	No adequate post-baseline assessment (including lost to follow-up since enrollment)	Date of first study treatment	Censored
2.3	Not known to have confirmed PD or died at the data analysis cutoff date (this includes subjects who were known to have confirmed PD or died after the data analysis cutoff date)	Date of last adequate disease assessment showing no evidence of confirmed PD on or before data analysis cutoff date	Censored
2.4	Addition of dexamethasone (Cohorts 1 and 3 ibrutinib monotherapy only)	The start date of dexamethasone	Censored

For subjects who meet more than one censoring condition, PFS will be censored according to the earliest censoring condition. For subjects who meet none of the censoring conditions, PFS will be calculated using the earliest event date.

$\text{PFS Event (day)} = \text{Date of PFS event} - \text{Date of first study treatment}$

$\text{PFS Censor (day)} = \text{Date of censoring} - \text{Date of first study treatment} + 1$

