8.8.3.3. Overall Survival (OS)

Overall survival (OS) will be measured from the date of first study drug administration until the date of death from any cause.

For subjects who have an incomplete death date, the death date will be imputed as the earliest possible date that incorporates the available death date information and that does not contradict the date last known alive in the database.

For subjects who were not known to have died prior to the analysis cutoff date, the overall survival will be right-censored based on the earliest censoring condition in Table 6.

OS Event (day) = Date of death – Date of first study treatment

OS Censor (day) = Date of censoring – Date of first study treatment + 1

Table 6: Date of Censoring for OS Analysis

Situation	Date of Censoring	Outcome
Not known to have died at the analysis cutoff date (this includes subjects who were known to have died after the data analysis cutoff date)	Date last known alive or data analysis cutoff date, whichever occurs first (specifically, for subjects who were known to have died after the data analysis cutoff date, overall survival will be censored at the data analysis cutoff date)	Censored

The date the subject was last known to be alive will be derived as follows:

- For subjects who became lost to follow-up when they were in the treatment phase, date last known alive will be derived using date of last assessment/visit, last dose date of study drug, or study exit date whichever occurs later;
- For subjects who became lost to follow-up when they were in the follow-up phase, date last known alive will be derived using date last known alive reported on the Follow-up CRF page or study exit date, whichever occurs later.

The same analyses (including subgroup analyses) will be done for OS as those for PFS described in Section 8.7.3.1.

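### For DCB, DOR, PFS, TTP and OS the SAP adds one day to censored times but not to event times; the effect on Kaplan-Meier estimates is small and can only be upward, and it goes away if the extra day is dropped.

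*SAP*

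**What the plan says.** SAP 8.8.3.2 gives TTP two formulas. For an event: "TTP Event (day) = Date of progression – Date of first study treatment". For a censored subject: "TTP Censor (day) = Date of censoring – Date of first study treatment + 1".

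The same pair appears for the other four endpoints:

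- DOR (SAP 8.8.2.3): "DOR Event (day) = Date of event – Date of first overall response" and "DOR Censor (day) = Date of censoring – Date of first overall response + 1".
- OS (SAP 8.8.3.3): the event time is date of death minus first treatment, but "OS Censor (day) = Date of censoring – Date of first study treatment + 1".
- DCB (SAP 8.8.2.1) and PFS (SAP 8.8.3.1): again no added day for an event and one added day for a censoring.

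All five are analysed by Kaplan-Meier, with medians. For PFS the SAP also names landmark rates at 4, 8, 12 and 16 months as examples. No reason is given for the two day counts, and protocol 8.3.3 and 8.3.4 contain no day-count formula. SAP 5.1 adds a day when it computes treatment duration and study day, but it does not make that depend on outcome.

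**The concern.** A time-to-event analysis should use one clock for everyone. Here a censored subject is carried one day beyond the last date on which the SAP regards that subject as observed. What that day is depends on the censoring rule:

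- For DCB, DOR and TTP, a death from causes other than progression is censored at the date of death (Table 4, row 2.5), so the subject remains at risk of progression on the day after death.
- For OS, censoring is at the earlier of last known alive and data cutoff, so the extra day can run past the cutoff.
- For the monotherapy analyses of Cohorts 1 and 3, censoring is at the start of dexamethasone (row 2.4 of Tables 4 and 5). SAP 8.3 ends the monotherapy period the day before, so the extra day goes further into combination treatment.

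At stake is a distortion in one direction, the favourable one, in the reported medians and landmark rates. It could be visible because disease assessments cluster around Day 1 (±2 days) of 28-day cycles, so events and censorings one day apart are plausible, and because cohorts have at most 43 subjects.

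**Working it through.** The documents give no expected value for these endpoints, so there is no planned figure to reproduce.

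**Direction (no assumptions needed).** Let u be an event time, d the number of events at u, n the number at risk at u when neither formula adds a day, and m the number censored on exactly day u − 1. Event times are the same under both rules. The SAP rule moves those m subjects to day u, where Kaplan-Meier counts them as at risk. The factor at u changes from 1 − d/n to 1 − d/(n + m). It can only stay the same or rise, and it rises only if m > 0. In 8,000 simulated datasets the curve was never lower under the SAP rule.

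**Date check.** First dose 1 March. Progression on 26 April gives an event time of 56 days. A last progression-free assessment on 25 April is 55 days later and gives a censored time of 55 + 1 = 56. The second subject is therefore counted as event-free on a day without observation.

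**Worked example (constructed data).** Ten subjects: events at days 28, 57, 57, 85, 113; censorings at days 28, 56, 56, 84, 112.

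| Event day | At risk, no added day | S | At risk, SAP rule | S |
|---|---|---|---|---|
| 28 | 10 | 9/10 = 0.90 | 10 | 0.90 |
| 57 | 6 | 0.90 × 4/6 = 0.60 | 8 | 0.90 × 6/8 = 0.675 |
| 85 | 3 | 0.60 × 2/3 = 0.40 | 4 | 0.675 × 3/4 = 0.506 |
| 113 | 1 | 0 | 2 | 0.506 × 1/2 = 0.253 |

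The median is 85 days without the added day and 113 days under the SAP rule. The data were chosen so that most censorings fall one day before an event. They show the mechanism, not the typical size. At day 28, where an event and a censoring fall on the same day, nothing changes.

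**Typical size (simulation; medians and censoring are assumed, not taken from the documents).** With 43 subjects, median PFS 140 days, visits every 28 days ±2, progression dated at the next visit and censoring at the last, the 8-month landmark is 8 × 30.4375 = 243.5 days (month length from SAP 5.10).

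| Censored | Mean rise in 8-month PFS (points) | Trials in which the median changed |
|---|---|---|
| 3% | about 0 | about 0 |
| 13% | 0.12 | 3% |
| 27% | 0.3 | 6% |
| 43% | 0.7 | 12% |
| 57% | 2.2 | 16% |

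In the last row everyone is censored between days 28 and 250 and the curve is read at day 243.5. Only about 1 of 43 subjects is still followed at day 224 or later, so 2.2 is a feature of the tail.

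A second set of assumptions had PFS medians of 5 or 10 months, 8 months for DCB, 50% to 68% censored, two-cycle visit spacing after the monthly visits, and 10, 18 or 43 subjects. It gave mean rises of 0.3 to 1.2 points across the four landmarks, with the 97.5th percentile at about 1 to 10 points. For OS (median 18 months, 63% to 73% censored) the mean rise was 0.01 to 0.12 points, and the median changed in under 1% of datasets.

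**The case against.** The strongest reply is that this is a one-day convention with almost no consequence. The final analysis comes at study completion, about five years in (protocol 7.3 and 8.7), and subjects who stop without progression are followed until progression or new therapy (protocol 7.1.4). Early administrative censoring should therefore be uncommon, although dropout or new therapy can still censor. DCB and DOR are secondary, and PFS, TTP and OS are exploratory. SAP 8.8 plans no inferential comparison among cohorts, and no decision rule uses these curves. All of this stands, and it limits the point to a minor correction.

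Several stronger readings are tempting, and the documents do not support them:

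- *That medians and landmark rates are inflated in every cohort.* Every cohort is exposed, but an estimate moves only when an event falls exactly one day after a censoring. In the first simulation the median was unchanged in 84% to 94% of trials at 27% to 57% censoring.
- *That giving d days to an event and d + 1 to a censoring on the same date is itself the bias.* It is not: a subject censored at d is already at risk for events at d.
- *That OS is materially biased.* The direction is the same, but the size is negligible.
- *That the expansion rule or the primary result is compromised.* Both rest on response counts, which use none of these formulas.

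It might also be said that adding a day to both formulas would match SAP 5.1. That is internally consistent, but it has a side effect, set out under the fix.

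**Conclusion.** The point holds as a small error in a stated rule, present in all five endpoints. Its direction is certain relative to omitting the added day: estimates are equal or higher, never lower. Its size depends on the assumed medians, visit pattern and censoring. On average it is about 0.1 to 0.7 percentage points on 8-month PFS at 10% to 43% censoring, more only when heavy censoring leaves few subjects followed near the landmark, and negligible for OS. A single small cohort can show several points or a shifted median, but most will not. Response rates, expansion decisions, significance level and power are untouched. It is worth correcting because it is cheap and the bias runs one way, not because it threatens a conclusion.

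**What to change.** Delete the added day from the censored-time formula in SAP 8.8.2.1, 8.8.2.3, 8.8.3.1, 8.8.3.2 and 8.8.3.3. Duration is then the date of event or censoring minus the start date for both outcomes. This also settles which formula applies to time on study, which SAP 8.2.1 defines as OS with the censoring reversed. The cost is one line per endpoint in the SAP and in the programs, with no new data. Estimates stay the same or become very slightly less favourable.

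Adding the day to both formulas would also give one clock, but it moves every event one day later. In simulation the median was then longer than under the SAP rule in 78% to 97% of trials, mostly by one day. A landmark near a visit window can rise too. Twelve months is 12 × 30.4375 = 365.25 days, and Cycle 14 Day 1 falls at elapsed day 13 × 28 = 364 (±2). An event at elapsed day 365 counts before the landmark now, but would become day 366 and fall after it. At about 27% censoring the SAP rule gave a 12-month PFS 0.8 points lower on average than adding the day to both. If the sponsor prefers that convention, the SAP should say so and should not describe it as making estimates less favourable.

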8.8.3.3. Overall Survival (OS)

Overall survival (OS) will be measured from the date of first study drug administration until the date of death from any cause.

For subjects who have an incomplete death date, the death date will be imputed as the earliest possible date that incorporates the available death date information and that does not contradict the date last known alive in the database.

For subjects who were not known to have died prior to the analysis cutoff date, the overall survival will be right-censored based on the earliest censoring condition in Table 6.

OS Event (day) = Date of death – Date of first study treatment

OS Censor (day) = Date of censoring – Date of first study treatment + 1

Table 6: Date of Censoring for OS Analysis

Situation	Date of Censoring	Outcome
Not known to have died at the analysis cutoff date (this includes subjects who were known to have died after the data analysis cutoff date)	Date last known alive or data analysis cutoff date, whichever occurs first (specifically, for subjects who were known to have died after the data analysis cutoff date, overall survival will be censored at the data analysis cutoff date)	Censored

The date the subject was last known to be alive will be derived as follows:

- For subjects who became lost to follow-up when they were in the treatment phase, date last known alive will be derived using date of last assessment/visit, last dose date of study drug, or study exit date whichever occurs later;
- For subjects who became lost to follow-up when they were in the follow-up phase, date last known alive will be derived using date last known alive reported on the Follow-up CRF page or study exit date, whichever occurs later.

The same analyses (including subgroup analyses) will be done for OS as those for PFS described in Section 8.7.3.1.

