#### **8.3.4.3 Overall Survival (OS)**

Overall survival (OS) is defined as the duration from first study drug administration until the date of death from any cause. Subjects who are known to be alive as of data analysis cutoff date will be censored at their date last known alive. Kaplan-Meier methodology will be used to estimate OS curves and corresponding quartiles (including the median). A 2-sided 95% confidence interval will be provided for the median OS.

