### **8.4 Handling of Missing Data**

Every effort will be made to collect all data. However, despite best efforts, it may be inevitable that missing or incomplete data are reported. All missing or partial data will be presented in the subject data listing, as they are recorded on the CRF.

Subjects lost to follow-up (or who dropped out) will be included in statistical analyses up to the point of their last evaluation. Unless otherwise specified, no imputation of values for missing data will be performed. Details of handling missing data will be included in the Statistical Analysis Plan.

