5.2. Time on Study

Time on study is defined as the interval between the date of the first dose of study drug and the date last known alive. Subjects who died will be censored at death date.

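### SAP 8.8.3.3 lets an undefined study exit date stand in for date last known alive in subjects lost to follow-up, which can raise estimated OS but never lower it

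*SAP*

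**What the plan says.** SAP 8.8.3.3 defines the endpoint conventionally: "Overall survival (OS) will be measured from the date of first study drug administration until the date of death from any cause". Its Table 6 censors subjects not known to have died at "Date last known alive or data analysis cutoff date, whichever occurs first".

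Two bullets then derive date last known alive, both for subjects who became lost to follow-up:

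- Lost in the treatment phase: the latest of the last assessment or visit, "last dose date of study drug, or study exit date whichever occurs later".
- Lost in the follow-up phase: "date last known alive reported on the Follow-up CRF page or study exit date, whichever occurs later".

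SAP 5.2 defines time on study as "the interval between the date of the first dose of study drug and the date last known alive", and SAP 8.2.1 reports its median by Kaplan-Meier with reversed censoring.

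The protocol is simpler. Section 8.3.4.3 states: "Subjects who are known to be alive as of data analysis cutoff date will be censored at their date last known alive". Section 8.4 states: "Subjects lost to follow-up (or who dropped out) will be included in statistical analyses up to the point of their last evaluation". Neither mentions study exit. The SAP introduction says changes to the protocol's analysis plan are documented in the SAP. Section 10 lists two, the added time-to-response endpoints and the major hemorrhage definition, and this is not one of them.

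**The concern.** Date last known alive should be the last date on which somebody had evidence that the subject was alive. A study exit date need not meet that test. In these documents it appears only as a disposition item with a reason attached (SAP 8.2.1) and in these two bullets. Nothing ties it to a contact.

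Under a later-of rule, the exit date has an effect only when it falls after every documented contact date. In the follow-up phase it then overrides the field on the Follow-up CRF that exists to record when the subject was last known alive. The extra interval counts as survival without an event, although nobody was observing whether a death occurred. If a death does become known, the subject is an event and the bullets do not apply, so only undetected time is credited.

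At stake are the OS curve, median, landmark and subgroup estimates for each cohort, and the reported length of follow-up. With at most 43 subjects per cohort, a few lost subjects can be a noticeable share.

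**Working it through.** **No figure to reproduce.** The documents give no assumed OS median, loss rate, OS event count or OS power. The check is therefore of direction first and then of size over an assumed range.

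**Direction.** The protocol's estimator is fixed: "Kaplan-Meier methodology will be used to estimate OS curves and corresponding quartiles (including the median"). At a time with one death and n subjects at risk, the curve is multiplied by 1 − 1/n. If k lost subjects are carried past their last contact to a later exit date, the factor becomes 1 − 1/(n + k), which is larger. For example, with n = 20 and k = 2 it moves from 1 − 1/20 = 0.950 to 1 − 1/22 = 0.955. Once the exit date is reached the risk sets agree again. No factor falls, so the OS curve and its median can only stay the same or rise.

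For time on study, each lost subject's recorded value can likewise only stay the same or lengthen. The reversed Kaplan-Meier median will generally follow, but this is not a strict rule, because there the moved date is an event and not a censoring.

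**Size: inputs.**

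- From the documents: Kaplan-Meier estimation, the later-of rule, the cap at data cutoff (Table 6), and at most 43 subjects per cohort (SAP 1.3).
- Assumed: exponential survival with a true median of 12 or 24 months; data cutoff uniform at 18 to 48 months; loss at random in 5%, 10% or 20%; exit 0, 3, 6 or 12 months after last contact, capped at cutoff, with no death recordable in the gap. There were 200,000 simulated subjects per setting.

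**Estimated median OS in months (shift from gap 0)**

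| True median | Lost | Gap 0 | Gap 3 | Gap 6 | Gap 12 |
|---|---|---|---|---|---|
| 12 | 5% | 11.95 | 12.08 (+0.13) | 12.18 (+0.23) | 12.29 (+0.34) |
| 12 | 10% | 12.01 | 12.29 (+0.28) | 12.52 (+0.51) | 12.78 (+0.77) |
| 12 | 20% | 11.98 | 12.56 (+0.58) | 13.10 (+1.12) | 13.79 (+1.81) |
| 24 | 5% | 24.01 | 24.17 (+0.16) | 24.33 (+0.32) | 24.62 (+0.61) |
| 24 | 10% | 24.05 | 24.42 (+0.37) | 24.78 (+0.73) | 25.43 (+1.38) |
| 24 | 20% | 24.03 | 24.83 (+0.80) | 25.62 (+1.59) | 27.10 (+3.07) |

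Censoring at last contact (gap 0) recovers the true median within simulation error. With a true median of 12 months, 24-month OS (true value 0.250) becomes 0.254-0.265 with 5% lost, 0.259-0.283 with 10% and 0.268-0.320 with 20%.

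**At cohort size.** In 4,000 simulated cohorts of 43 with 6 lost and a 6-month gap, mean 12-month OS rose from 0.533 to 0.556, mean 24-month OS from 0.274 to 0.294 and the mean estimated median from 13.4 to 14.3 months. No cohort's estimate fell. These pairs should be read only as contrasts between the two rules. The starting values exceed 0.500, 0.250 and 12 partly because this run placed each loss at a random fraction of the subject's own follow-up.

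**The case against.** **The premise is conditional.** Study exit date is undefined, so a CRF convention could set it to the date of last contact. The bias is then exactly zero. A reader might infer that the date is administrative, entered when a site closes the record, and that OS is therefore certainly overstated. The documents do not say so. They leave the date undefined, which permits the bias without establishing it. This stands.

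**The gap has no documented minimum.** A reader might infer from the 3-monthly survival contacts that any loss implies a gap of about 3 months or more. That interval (Protocol Appendix 4, footnote d) covers only long-term follow-up after progression or new therapy, and Amendment 5 ends it after a minimum of one visit. Treatment visits come once per 28-day cycle and then every 2 cycles (Protocol 7.1.2), and response follow-up about every 2 months (7.1.4). A contact schedule also does not fix the lag to an undefined exit date. This stands, and short gaps give small shifts: about 0.1 month or less on a 12-month median with 5% lost and a gap of 1 to 2 months.

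**OS carries little weight here.** It is exploratory, and SAP 8.8 rules out inferential comparison between cohorts. With 43 subjects and a true median of 12 months, the estimated median already ranges over roughly 7.5 to 18 months by chance. This limits the consequence. But sampling error averages out and this error does not, since it always runs in the favorable direction.

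**The protocol leaves room.** Section 8.4 defers missing-data details to the SAP, and 8.3.4.3 speaks literally of subjects known to be alive at cutoff. The first point allows the SAP to add detail, but not to extend lost subjects past their last evaluation without saying so. The second means that the plain conflict is with 8.4, while 8.3.4.3 is departed from in substance.

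**An exit date can be evidence of life.** A subject who withdraws consent in person, or rolls over to another study, was alive that day. This stands and shapes the fix.

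**Conclusion.** The concern holds in conditional form. SAP 8.8.3.3 allows a date with no required evidence of life to replace the last documented contact, in one direction only and without declaring the departure from the protocol.

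The effect on median OS, for an assumed 12-month median and gaps of 3 to 12 months, is about 0.1-0.3 months with 5% lost, 0.3-0.8 with 10% and 0.6-1.8 with 20%. It is zero if exit equals last contact. For an assumed 24-month median the shifts are about 0.2-0.6, 0.4-1.4 and 0.8-3.1 months. These ranges rest on assumed loss rates, gaps, exponential survival and non-informative loss. The documents cannot say which row applies.

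The reach is limited to exploratory OS and descriptive time on study. CBR and the Simon decision rules do not use this date. DCB, DOR, TTP and PFS are censored by separate rules based on disease assessments (SAP Tables 4 and 5).

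**What to change.** In both bullets of SAP 8.8.3.3, remove study exit date unless contact with the subject on that date is documented. Derive date last known alive only from documented evidence of life: the last visit, assessment or dose, or the last-known-alive date on the Follow-up CRF. Use the same date for time on study (SAP 5.2 and 8.2.1).

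Table 6 covers everyone not known to have died, while the two bullets cover only lost subjects. Stating that the same derivation applies to all censored subjects would close that gap in the same edit.

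The cost is two phrases in the SAP and one derivation line in the program. Recorded OS follow-up becomes slightly shorter for some lost subjects. If exit already equals last contact in the data, no result changes.
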